7.12.2 Clinical Laboratory Evaluations

For the purposes of summarization, all laboratory values will be converted to standardized units. If a lab value is reported using a non-numeric qualifier (eg, less than (<) a certain value, or greater than (>) a certain value), the given numeric value will be used in the summary statistics, ignoring the non-numeric qualifier.

If a patient has repeated laboratory values for a given time point, the value from the last evaluation will be used. Laboratory test results will be summarized according to the scheduled sample collection time point. Change from baseline will be presented. Scheduled laboratory along with unscheduled lab test results will be listed.

Lab parameters to be analyzed are as follows:

- Hematology: Hemoglobin, Lymphocyte count, Neutrophil count, Platelet count, White blood cell count.
- Chemistry: albumin, alanine aminotransferase (ALT), alkaline phosphatase (ALP), aspartate aminotransferase (AST), bilirubin (total), corrected calcium, creatinine, glucose, potassium, sodium.

Whenever available, laboratory values will be assigned toxicity grades using the NCI CTCAE Version 5.0. Shift tables will be constructed for laboratory parameters either using CTCAE grade or based on low/medium/high compared to normal ranges on patients who have both baseline and at least one post-baseline assessment. Individual platelet and ANC profiles will be generated for each schedule/dose level. Mean values over time for platelets and ANC will be produced for the expansion cohort only.

7.12.3 Vital Signs

For dose escalation cohorts, descriptive statistics for vital sign results (diastolic and systolic blood pressure, respiratory rate, pulse rate, oxygen saturation and body weight) will be summarized by schedules and dose levels as follows:

- Baseline value (C1D1 or screening if C1D1 is not available).
- Minimum post-baseline value.
- Change to Minimum post-baseline value.
- Maximum post-baseline value.
- Change to Maximum post-baseline value.

Changes to the minimum and maximum post-baseline values will be calculated relative to the baseline value.

For blood pressure values collected during the infusion, the number and percentage of patients with changes from pre-infusion blood pressure values will be summarized in the following categories:

- Increase of diastolic blood pressure of at least 10 mm Hg during any infusion.
- Decrease of diastolic blood pressure of at least 10 mm Hg during any infusion.
- Increase of systolic blood pressure of at least 20 mm Hg during any infusion.
- Decrease of systolic blood pressure of at least 20 mm Hg during any infusion.

For expansion and extension cohorts, descriptive statistics for vital sign results will be summarized by visit up to end of treatment (EOT) visits (including visits where blood pressure was measured every 30 minutes during the first 4 infusions, and after the end of the infusion). In addition, a summary of diastolic blood pressure and systolic blood pressure during the infusion will be summarized as described above for escalation cohorts.

7.12.4 12-Lead ECGs

ECG data (ventricular rate, RR interval, PR interval, QT interval, and QTcF interval) will be summarized by schedules and dose levels as follows:

- Baseline value (C1D1 or screening if C1D1 is not available).
- Minimum post-baseline value.
- Change to Minimum post-baseline value.
- Maximum post-baseline value.
- Change to Maximum post-baseline value.

Changes to the minimum and maximum post-baseline values will be calculated relative to the baseline value.

In addition, a categorical analysis of QTcF intervals will be performed for each time point. The number and percentage of patients in each QTcF interval (<450 msec, 450-480 msec, >480-
<500 msec, and \geq 500msec) will be summarized at baseline and each of the subsequent time points. Categories of changes from baseline (\geq 30 msec and \geq 60 msec) will be summarized as well.

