9.3.9.4 ECGs

A 12-lead ECG will be administered at the time points specified in the SOEs (Appendix A). A qualified person will interpret the ECG. In Parts 1 and 2, triplicate ECGs will be read centrally, and single ECGs will be read locally. When the timing of triplicate and single (safety) ECGs coincide, the site can use the triplicate ECG collection for safety evaluation.

Any ECG finding that is judged by the investigator as clinically significant (except at the screening visit) will be considered a TEAE, recorded on the source documentation and in the eCRF, and monitored as described in Section 10.2.

In Parts 1 and 2, triplicate ECGs for initial heart rate-corrected QT interval evaluation will be recorded and electronically stored at prespecified time points. These time points correspond with PK draws. Please refer to the PK Sampling Schedules (Appendix C).

The ECG measurements should be completed before the PK/ pharmacodynamic blood draw. It is recommended that patients refrain from eating or limit themselves to bland food for 1 hour before dosing and until completion of the scheduled ECG measurements (4 hours after dosing).

In Part 3, all patients will have single ECGs collected and read locally at screening, at the end of the infusion (+30 minutes), or in accordance with the SOEs in Appendix A.

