13.1.8 Safety Analysis

The safety and tolerability of modakafusp alfa will be assessed by the recording of TEAEs (using NCI CTCAE, Version 5.0), vital signs, physical examination, chemistry, hematology, urinalysis, ECG, and concomitant medications.

TEAEs will be summarized using the safety analysis set and will be coded using the MedDRA. Data will be summarized using preferred terms and the primary SOC.

All patients receiving at least 1 dose of modakafusp alfa will be considered evaluable for the safety analysis. The AE incidence rates and the frequency of occurrence of overall toxicity, categorized by toxicity grades (severity), will be presented. Listings of laboratory test results and vital signs will be generated. Descriptive statistics summarizing the changes in laboratory tests over time will be reported.

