ADA: antidrug antibody; AE: adverse event; ALT: alanine aminotransferase; anti-HBs: antibodies to hepatitis B surface antigen; AST: aspartate aminotransferase; BMA: bone marrow aspiration; C: cycle; CO2: carbon dioxide; CR: complete response; CT: computed tomography; D, d: day; ECG: electrocardiogram; ECOG: Eastern Cooperative Oncology Group; EORTC QLQ-MY20: European Organisation for Research and Treatment of Cancer QLQ Questionnaire Multiple Myeloma Module; EOT: end of treatment; EQ-5D-5L: EuroQoL-5 Dimensions-5 Levels; FLC: free light chain; FU: follow-up; HBsAg: hepatitis B surface antigen; HBV: hepatitis B virus; HCO3-: bicarbonate; ICF: informed consent form; LDH: lactate dehydrogenase; MRD: minimal residual disease; MRI: magnetic resonance imaging; PBMC: peripheral blood mononuclear cells; PCR: polymerase chain reaction; PD: progressive disease; PET-CT:

positron emission tomography-computed tomography; PFS: progression-free survival; PK: pharmacokinetic(s); PRO: patient-reported outcome; q12wk: every 12 weeks; SAE: serious adverse event; TBNK: T-lymphocyte, B-lymphocyte, and natural killer cells; V: visit; WBC: white blood cell.

Note: Crosses in parentheses "(X)" indicate tests are to be performed only under certain circumstances as indicated in associated footnote(s).

- a. Written informed consent must be obtained before performing any protocol-specific procedure. Test results from routine clinical management are acceptable for screening if obtained within the specified time window.
- b. Height will be measured only at the screening visit.
- c. All patients will have 1 standard local ECG collected and read locally at screening and at the end of the infusion (+30 minutes) on the days indicated.
- Vital signs measured before starting the infusion and after the completion of the infusion. Vital signs include temperature, pulse, respiratory rate, oxygen saturation, and blood pressure. Blood pressure will be measured every 30 minutes (±5 minutes) during the first 4 infusions, after the end of the infusion, and at any time a patient complains of symptoms consistent with IRR.
- e. Clinical imaging assessments to summarize status of known lesions should be based on available imaging at each respective time point.

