7.1 General Principles

All statistical analyses will be conducted using SAS[®] Version 9.4 or later.

For categorical variables, the count and proportions of each possible category value will be tabulated. The denominator for the proportion will be based on the number of subjects in the analysis sets. For continuous variables, the mean, median, standard deviation, minimum, and maximum values will be presented for all patients in the relevant analysis set.

Means and medians will be presented to 1 more decimal place than the recorded data. The standard deviations will be presented to 2 more decimal places than the recorded data.

Confidence intervals about a parameter estimate will be presented using the same number of decimal places as the parameter estimate.

All confidence intervals, statistical tests, and resulting P-values will be reported as 2-sided. P-values should be presented to 3 decimal places, with values less than 0.001 presented as <0.001.

Baseline values are defined as the last observed value before the first dose of study drug.

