7.12 Safety Analysis

For Part 3 extension cohorts, analysis and review will assess the safety data across the treatment arms as well as in the patients with low body weight. Data to be reviewed will be summarized by treatment arm as well as by body weight (e.g., ≤ 80 kg and > 80 kg). With additional cumulative data, the weight subgroups may be further subdivided. The data might be included in the CSR if there is a safety trend identified in a specific low body weight group.

CONFIDENTIAL

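### The ECG baseline rule in SAP 7.12.4 omits predose, so read literally it uses an end-of-infusion ECG as the Part 3 baseline

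*SAP*

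**What the plan says.** SAP 7.12.4 (12-Lead ECGs) lists the summaries for ventricular rate and the RR, PR, QT and QTcF intervals. The first item is the baseline: "Baseline value (C1D1 or screening if C1D1 is not available"). Changes to the minimum and maximum post-baseline values are calculated from it, and changes in QTcF from baseline are also categorised at 30 and 60 msec. The subsection has no cohort limit.

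SAP 7.1 (General Principles) gives a rule for the whole plan: "Baseline values are defined as the last observed value before the first dose of study drug".

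Protocol 9.3.9.4 sets the Part 3 timing: "In Part 3, all patients will have single ECGs collected and read locally at screening, at the end of the infusion (+30 minutes"), or as the schedule of events directs. The Part 3 schedule (Appendix A, Tables 12 and 13, footnote c) agrees: "All patients will have 1 standard local ECG collected and read locally at screening and at the end of the infusion (+30 minutes") on the marked days. Table 12 has a single ECG row, marked at screening, C1D1, C1D8, C1D15 and C2D1. Table 13 adds one at end of treatment. There is no predose or triplicate ECG row.

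**The concern.** The ECG bullet names a visit but not a time within it, and it ranks C1D1 ahead of screening. In global Part 3 the C1D1 ECG follows the first infusion. A programmer who implements the bullet as written will therefore flag a post-dose reading as baseline for almost every patient.

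Two things follow. Every change from baseline is measured from a reading that may already contain an acute drug effect. The C1D1 end-of-infusion ECG also stops being a post-baseline observation, which leaves C2D1 as the only scheduled end-of-infusion ECG in the change summaries. An acute effect of similar size at each infusion would cancel out of the C2D1 change.

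**Working it through.** **Which ECG each rule selects (global Part 3 patient)**

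| Scheduled ECG | Timing | SAP 7.12.4, literal | SAP 7.1 |
|---|---|---|---|
| Screening | before first dose | fallback only | baseline |
| C1D1 | end of infusion | baseline | post-baseline |
| C1D8, C1D15 | no infusion that day | post-baseline | post-baseline |
| C2D1 | end of infusion | post-baseline | post-baseline |
| End of treatment | no infusion | post-baseline | post-baseline |

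Five ECGs follow the start of dosing, two of them at end of infusion. The literal rule leaves four post-baseline ECGs, one of them at end of infusion.

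**Whether 7.12.4 reaches Part 3**

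- The same bullet appears in SAP 7.12.3 for vital signs, but there it is confined to the dose-escalation cohorts. 7.12.4 has no such limit.
- The opening of SAP 7.12 brings Part 3 in: "For Part 3 extension cohorts, analysis and review will assess the safety data across the treatment arms". Protocol 13.1.8 lists the safety measures without a Part limit: "vital signs, physical examination, chemistry, hematology, urinalysis, ECG, and concomitant medications".
- For vital signs the bullet is harmless, because a value before infusion exists: "Vital signs measured before starting the infusion and after the completion of the infusion". SAP 7.12.3 also states the timing where it matters: "changes from pre-infusion blood pressure values will be summarized in the following categories". 7.12.4 does not.

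**Other cohorts**

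- Parts 1 and 2 have a predose C1D1 triplicate ECG from Cohort 3 (0.1 mg/kg), or earlier if a biological effect was seen. The gap remains for Part 1 cohorts treated before triplicates began.
- The French country-specific text (Protocol Appendix J) adds a Part 3 ECG before the infusion. The point therefore concerns the global schedule.

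**Illustrative size**

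The documents give no QTcF effect or variability. Assumptions: independent normal readings, within-patient SD s = 8 to 15 msec, and an acute effect d at C1D1 and C2D1 only.

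Mean change to maximum, by numerical integration of the expected maximum of independent normals:

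- Predose baseline, five ECGs: E[max] of five readings with means (d, 0, 0, d, 0).
- C1D1 end-of-infusion baseline, four ECGs: E[max] of four readings with means (0, 0, d, 0), minus d, because the baseline itself contains d.

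| | s = 8, d = 0 | s = 8, d = 10 | s = 15, d = 0 | s = 15, d = 10 |
|---|---|---|---|---|
| Predose baseline, 5 ECGs | 9.30 | 15.46 | 17.44 | 22.63 |
| Predose baseline, same 4 ECGs | 8.24 | 12.58 | 15.44 | 18.89 |
| End-of-infusion baseline, 4 ECGs | 8.24 | 2.58 | 15.44 | 8.89 |

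A 10 msec effect raises the summary by 6.2 msec (15.46 − 9.30) or 5.2 msec (22.63 − 17.44) with a predose baseline. With the end-of-infusion baseline it lowers the summary by 5.7 msec (8.24 − 2.58) or 6.6 msec (15.44 − 8.89). On the same four ECGs the gap between the two baselines equals d: 12.58 − 2.58 = 10 and 18.89 − 8.89 = 10. With no effect that gap is zero. The non-zero values at d = 0 come only from taking the maximum of noisy readings.

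Probability of a change of at least 30 msec at C2D1, where the change has SD s√2 = 11.3 or 21.2 msec:

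- Predose baseline: 1 − Φ((30 − d)/(s√2)). This gives 0.4% and 7.9% at d = 0, and 3.9% and 17.3% at d = 10.
- End-of-infusion baseline: 1 − Φ(30/(s√2)). This gives 0.4% and 7.9% whatever d is.

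**The case against.** The strongest reply is that 7.1 is a general principle with no exception, and 7.12.4 is silent on time within the visit. The two can be read together: use a C1D1 ECG taken before dosing if there is one, otherwise screening. That reading is available and may be what the sponsor intends. But 7.12.4 does not refer to 7.1, a section-specific rule would normally displace a general one, and the reading has to treat a C1D1 ECG that was scheduled and recorded as not available for nearly every global Part 3 patient.

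A second reply is that Part 3 coverage is inferred. 7.12.4 summarises by schedule and dose level, which resembles the Part 1 and 2 layout, and QTcF is a named endpoint only in Parts 1 and 2. This is weak: SAP 7.12.1 uses the same layout wording for adverse events and expressly includes the extension cohorts.

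A third reply concerns size, and much of it stands. The example assumes an effect that recurs equally at both infusions and is absent at other visits, which is the pattern most easily masked. At 5 msec the probability of a 30 msec change at C2D1 is 1.4% to 12% with a predose baseline, against 0.4% to 8%. For the 60 msec category at a 10 msec effect it is at most 0.9% against at most 0.2%. The absolute QTcF categories would still show a high C1D1 value, though in the baseline column. Clinically significant ECG findings are recorded as TEAEs under Protocol 9.3.9.4. No primary, secondary or stopping analysis depends on these tables.

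**Conclusion.** The concern holds. As written, 7.12.4 and 7.1 select different baselines for a global Part 3 patient, and the literal ECG rule takes a post-dose reading. That this reading is post-dose follows from the schedule and needs no assumption. How much it distorts the tables depends on an acute effect that the documents do not quantify. If such an effect recurs equally at C1D1 and C2D1, it is subtracted out of the C2D1 change in full; if there is none, the only difference is one fewer post-baseline ECG. The consequence is confined to descriptive safety tables. It is still worth correcting, because two programmers following the current text could produce different change-from-baseline tables.

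**What to change.** Replace the baseline bullet in SAP 7.12.4 with:

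> Baseline = last ECG before the first dose of study drug, per Section 7.1 (C1D1 predose ECG where one was taken, otherwise screening); any C1D1 ECG taken after the start of infusion is post-baseline.

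If the sponsor already means 7.1 to govern, this line simply says so. The cost is one SAP line and one baseline flag for Part 3. No new data are needed, since a screening ECG is scheduled for every patient. For Parts 1 and 2 the sponsor should also state how triplicates are used (averaging, and central against local reads), because triplicates are read centrally and single ECGs locally. That choice is the sponsor's.

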7.12.5 Other Observations Related to Safety

Shifts from baseline to the worst post-baseline ECOG score will be tabulated.

7.13 Interim Analyses and Criteria for Early Termination

Part 2

A futility analysis will be conducted when 10 response-evaluable patients in a phase 2 arm have been followed for at least 3 cycles or have already responded or withdrawn. An arm with the predictive probability <15% (i.e., 3 or fewer responders in 10 patients) will stop enrollment for futility. Overall, avoidance of futility requires 11 or more responders out of the 25 patients to achieve 90% of the overall posterior probability of success (PPOS) at the final analysis. Unless all 25 patients have already been enrolled, another futility analysis with the same decision rule based on PPOS will be conducted when 15 response-evaluable patients in a phase 2 arm have been followed for at least 3 cycles or have already responded or withdrawn. If there are 5 or fewer responders in 15 patients, enrollment will stop for futility. However, the study team reserves the rights to continue the study if the patients still benefit from the study drug.

Part 3

In the Part 3 extension cohorts, an independent data monitoring committee (DMC) will review accumulating safety, tolerability, and efficacy data. The first DMC meeting will occur after approximately 20 patients (approximately 10 patients from each arm) have been enrolled and treated. The second and third DMC meeting will occur at the first and second interim futility analysis when approximately 30 and 96 patients (approximately 15 and 48 patients from each arm) have been enrolled and have completed 3 cycles of treatment or discontinue the treatment prematurely. The subsequent DMC meetings will be approximately every 6 months thereafter.

Futility Stopping Rules

Two interim analyses for futility are planned for the Part 3 extension cohorts when approximately 15 and 48 patients of the planned 118 patients per arm are enrolled and treated for at least 3 cycles or have discontinued treatment prematurely. The futility stopping boundary will be determined based on the predictive probability of success at the primary analysis, using a Bayesian efficacy monitoring approach. The treatment arm will be dropped for futility if the predictive probability of success at the primary analysis is found to be <10% based on the data

CONFIDENTIAL

from the interim analysis. Various prior distributions for the ORR are used for each treatment arm due to different prior efficacy information at different dose levels collected in Parts 1 and 2 of the study. Based on the data cutoff of October 22, 2021, the observed ORR was 40% for the overall 30 patients enrolled in 1.5 mg/kg cohorts including both escalation and expansion cohorts. To reflect the prior information for the 120 mg arm collected in the Part 1 and Part 2, a weakly informative prior of Beta (1.2, 1.8) is used for the 120 mg arm. This will translate to a Beta prior with a response rate of 40% based on the information of 3 patients (10% of the sample size in Part 1 and 2). However, because of comparatively limited efficacy data available at the 3 mg/kg (240 mg) dose, a noninformative prior of Beta (0.5, 0.5) is used. Based on these prior distributions, Table 3 shows the stopping rules used for the treatment arms of 240 mg and 120 mg at each interim futility analysis based on the prespecified number of patients. The actual futility boundaries will be recalculated based on the observed number of treated patients at each interim futility analysis using the same posterior probability stopping rule if it is different from the planned number of patients. The details of the operating characteristics of the futility stopping rules are described in Appendix D.

There is no plan to stop for efficacy based on the interim analysis data.

Table 3 Stopping Boundaries for 240mg and 120mg Arms at Each Interim Futility Analysis

	Number of patients enrolled and followed up for 3 months	Recommend terminating the corresponding treatment arm due to lack of efficacy when number of responders is:	
		240mg Arm	120mg Arm
1st Interim Futility Analysis	15	≤2	≤1
2nd Interim Futility Analysis	48	≤10	≤10

Continuous Safety Monitoring Plan and Stopping Rules

Grade ≥ 4 nonhematologic treatment-related TEAEs, as well as treatment-related deaths, will be continuously monitored at the following timepoints using a Bayesian toxicity monitoring approach based on posterior probability (Table 4).

Table 4 Safety Monitoring Time Points Based on Bayesian Stopping Rules

	Timepoint
1st DMC safety review	20 patients have been treated (10 patients in each arm)
2nd DMC safety review (first interim futility analysis)	15 patients in each arm treated for at least 3 cycles or discontinued treatment prematurely

3rd DMC safety review (second interim futility analysis)	48 patients in each arm treated for at least 3 cycles or discontinued treatment prematurely
---	---

The stopping rules will be determined based on the posterior probability of the unacceptable toxicity event rate $>25\%$, and the unacceptable treatment-related death rate $>5\%$. If there is at least an 80% probability that the true toxicity event (Grade ≥ 4 nonhematologic treatment-related TEAEs) rate is greater than 25% given the observed toxicity data, the enrollment will be paused until the IDMC reviews the data to avoid putting more patients at risk. Similarly, if there is at least an 80% probability that the true treatment-related death rate is greater than 5% given the observed death data, enrollment will be paused until the IDMC reviews the data. Details of the Bayesian toxicity monitoring plan and the operating characteristics can be found in Appendix E.

